2.6 Interim Analysis

An interim analysis will be performed once all subjects in Treatment Group complete the 12 Months visit after last treatment (or discontinued before) and all subjects in Control Group complete the 6 months visit after last treatment (or discontinued before).

2.7 Determination of Sample Size

CCI

CCI

To account for 15% dropouts, approximately 111 will be randomized to the Restylane Defyne Treatment Group and approximately 37 to the Control group.

**Table A 2. Analysis populations (all randomized subjects)**

Site	Subject number	Safety		FAS		PP	
		n	%	n	%	n	%
PPD	xx	xx.X		xx	xx.X	xx	xx.X
	xx	xx.X		xx	xx.X	xx	xx.X
	xx	xx.X		xx	xx.X	xx	xx.X
	xx	xx.X		xx	xx.X	xx	xx.X
	xx	xx.X		xx	xx.X	xx	xx.X
	xx	xx.X		xx	xx.X	xx	xx.X
Total (N)	-	xx	100.0	xx	100.0	xx	100.0

% = 100*n/N

**Table A 3. Subject accountability (all subjects in Restylane Defyne group)**

Number of subjects	Observed	Missed	Withdrawals	Continuing on study
Baseline/initial treatment	xx	xx	xx	xx
4W follow up/optional touch-up	xx	xx	xx	xx
4W follow up after last treatment	xx	xx	xx	xx
3M after last treatment	xx	xx	xx	xx
6M after last treatment	xx	xx	xx	xx
9M after last treatment	xx	xx	xx	xx
12M after last treatment	xx	xx	xx	xx

Table A 4. Subject accountability (all subjects in Control group)

Number of subjects	Observed	Missed	Withdrawals	Continuing on study
Baseline	xx	xx	xx	xx
4W follow up after randomization	xx	xx	xx	xx
3M after randomization	xx	xx	xx	xx
6M after randomization /treatment	xx	xx	xx	xx
4W follow up/optional touch-up	xx	xx	xx	xx
4W follow up after last treatment	xx	xx	xx	xx
3M after last treatment	xx	xx	xx	xx
6M after last treatment	xx	xx	xx	xx
9M after last treatment	xx	xx	xx	xx
12M after last treatment	xx	xx	xx	xx

**Table A 5. Withdrawn subjects**

Site	Subject number	Group	Date of treatment		Last visit performed	Date of last visit performed	Date of withdrawal	Reason for withdrawal
			Treatment	Optional touch up				

Table A 6. Protocol deviations affecting PP population

Protocol deviation (category)	Number of subjects/subject number	Number of deviations

Table A 7. Protocol deviations not affecting PP population

Protocol deviation (category)	Number of subjects/subject number	Number of deviations

**Table A 8. Demographic and baseline characteristics (FAS)**

Variable	Parameter	Restylane Defyne N = XX	Control N = XX	Total N = XX
Age (years)	N	xx	xx	xx
	Mean	xx.x	xx.x	xx.x
	SD	xx.x	xx.x	xx.x
	Median	xx.x	xx.x	xx.x
	Minimum	xx.x	xx.x	xx.x
	Maximum	xx.x	xx.x	xx.x
Gender	Female	n (%)	xx (xx.x)	xx (xx.x)
	Male	n (%)	xx (xx.x)	xx (xx.x)
Ethnic Origin	Han Chinese	n (%)	xx (xx.x)	xx (xx.x)
	Other*	n (%)	xx (xx.x)	xx (xx.x)
Baseline GCRS**	1 Mild retrusion	n (%)	xx (xx.x)	xx (xx.x)
	2 Moderate retrusion	n (%)	xx (xx.x)	xx (xx.x)

% = 100*n/N

* Other: xxx

** As evaluated by the Blinded Evaluator

**Table A 9. Subjects reporting medical history/concurrent disease and number of conditions by the MedDRA System Organ Class (FAS)**

	Restylane Defyne N=xx						Control N=xx					
	All		Ongoing at study start		All		Ongoing at study start		Subjects		Conditions	
Primary SOC	Subjects	Conditions	Subjects	Conditions	Subjects	Conditions	Subjects	Conditions	n	%	n	
	n	%	n	%	n	%	n	%	n	%	n	
	xx	xx.x	xx	xx	xx.x	xx	xx	xx.x	xx	xx.x	xx	
	xx	xx.x	xx	xx	xx.x	xx	xx	xx.x	xx	xx.x	xx	
Total*	xx	xx.x	xx	xx	xx.x	xx	xx	xx.x	xx	xx.x	xx	

%₀= 100*n/N

* A single subject may have reported medical history (relevant or major illness) by more than one primary SOC category

Table A 10. Prior use of facial fillers or implants (FAS)

Facial filler/implant	Restylane Defyne N=xx		Control N=xx	
	Subjects		Subjects	
	n	%	n	%
Hyaluronic Acid (HA)	xx	xx.x	xx	xx.x
Permanent implant	xx	xx.x	xx	xx.x
Semi-permanent implant	xx	xx.x	xx	xx.x
.	xx	xx.x	xx	xx.x
.	xx	xx.x	xx	xx.x
.	xx	xx.x	xx	xx.x
Total	xx	xx.x	xx	xx.x

%₀=100*n/N**Table A 11. Prior use of other facial dermatological procedures (FAS)**

Facial dermatological procedure	Restylane Defyne N=xx		Control N=xx	
	Subjects		Subjects	
	n	%	n	%
Butolinum toxin injection	xx	xx.x	xx	xx.x
Resurfacing	xx	xx.x	xx	xx.x
Mesotherapy	xx	xx.x	xx	xx.x
.	xx	xx.x	xx	xx.x
.	xx	xx.x	xx	xx.x
.	xx	xx.x	xx	xx.x
Total	xx	xx.x	xx	xx.x

%₀=100*n/N

**Table A 12. Subjects reporting concomitant medication (FAS)**

Concomitant medication	Any concomitant medication?							
	Restylane Defyne N=xx				Control N=xx			
	No		Yes		No		Yes	
	n	%	n	%	n	%	n	%
Ongoing at study start								
Initiated during study								
Total								

%=100*n/N

Table A 13. Subjects reporting concomitant medication and number of medications by reason (FAS)

Reason for concomitant medication	Restylane Defyne N=xx				Control N=xx			
	Subjects		Medications		Subjects		Medications	
	n	%	No. of medications		n	%	No. of medications	
Medical History	xx	xx.x	xx		xx	xx.x	xx	
Adverse Event	xx	xx.x	xx		xx	xx.x	xx	
Other	xx	xx.x	xx		xx	xx.x	xx	

%=100*n/N

Table A 14. Subjects reporting concomitant medication and number of medications by ATC code (FAS)

ATC code	ATC text	Restylane Defyne N=xx				Control N=xx			
		Subjects		Medications		Subjects		Medications	
		n	%	No. of medications		n	%	No. of medications	
		xx	xx.x	xx		xx	xx.x	xx	
		xx	xx.x	xx		xx	xx.x	xx	

%=100*n/N

**Table A 15. Concomitant medication taken due to an AE by ATC code (FAS)**

Concomitant medication			Adverse event	
ATC text (ATC code)	No. of subjects	No. of medications	MedDRA Preferred term	Related
ATC 1	xx	xx	PT 1	Yes/No
ATC 1	xx	xx	PT 2	Yes/No
ATC 1	xx	xx	PT 3	Yes/No
ATC 1	xx	xx	PT 4	Yes/No
ATC 2	xx	xx	PT 1	Yes/No
ATC 3	xx	xx	PT 1	Yes/No
.	xx	xx	.	Yes/No
Total	xx	xx	-	-

Table A 16. Subjects reporting concomitant procedure/treatment by reason (FAS)

	Restylane Defyne N=xx			Control N=xx		
	No. of subjects		No. of procedures/treatments	No. of subjects		No. of procedures/treatment
Reason for concomitant procedure/treatment	n	%		n	%	
Medical history	xx	xx.x	xx	xx	xx.x	xx
Adverse event	xx	xx.x	xx	xx	xx.x	xx
Other	xx	xx.x	xx	xx	xx.x	xx
Total	xx	xx.x	xx	xx	xx.x	xx

%=100*n/N

**Table A 17. GCRS responder rate by treatment at Month 6, Blinded Evaluator (FAS)**

Time point	Treatment group	# of subjects in FAS	# of responders	Proportion of responders	95% confidence interval	P-value
6 month after last treatment	Restylane Defyne	xx	xx	x.xx	x.xx, x.xx	
6 month after randomization	Control	xx	xx	x.xx	x.xx, x.xx	
Difference	-			x.xx	x.xx, x.xx	x.xx

Note: Subjects with a missing GCRS have their values imputed using BOCF at Month 6

Note: Responder is defined as a subject with an improvement of at least one grade on the GCRS from baseline

Note: Responder rate is calculated as the number of Responders divided by the number of subjects in the FAS population for the specific treatment group.

Note: P-values for the difference in proportions are based on the Fisher's Exact test

Note: 95% Confidence Intervals are two-sided and calculated using the binomial distribution

Table A 18. GCRS responder rate by treatment at Month 6, Blinded Evaluator (PP)

As Table A 17.

Note: No imputation is used for the PP analysis. Only subjects with complete data are included.

Note: Responder is defined as a subject with an improvement of at least one grade on the GCRS from baseline

Note: Responder rate is calculated as the number of Responders divided by the number of subjects in the FAS population for the specific treatment group.

Note: P-values for the difference in proportions are based on the Fisher's Exact test

Note: 95% Confidence Intervals are two-sided and calculated using the binomial distribution

Table A 19. Sensitivity analysis for the GCRS responder rate by treatment at Month 6, Blinded Evaluator (FAS)

As Table A 17.

Note: Subjects with a missing GCRS have their values imputed using the hot deck method at Month 6

Note: Responder is defined as a subject with an improvement of at least one grade on the GCRS from baseline

Note: Responder rate is calculated as the number of Responders divided by the number of subjects in the FAS population for the specific treatment group.

Note: P-values for the difference in proportions are based on the Fisher's Exact test

Note: 95% Confidence Intervals are two-sided and calculated using the binomial distribution

Table A 20. Logistic regression, Blinded Evaluator (FAS)

Parameter	Coefficient	SE	Wald Chi-Square	Degrees of freedom	P-value
Baseline GCRS	x.xx	x.xx	x.xx	x	x.xx
Treatment Group	x.xx	x.xx	x.xx	x	x.xx

Title

Statistical Analysis Plan 43CH1627 - Chin

Doc id

MA-38115**Table A 21. GCRS responder rate by treatment at Month 3, Blinded Evaluator (FAS)**

As Table A 17.

Note: Subjects with a missing GCRS are not imputed

Note: Responder is defined as a subject with an improvement of at least one grade on the GCRS from baseline

Note: Responder rate is calculated as the number of Responders divided by the number of subjects in the FAS population for the specific treatment group.

Note: P-values for the difference in proportions are based on the Fisher's Exact test

Note: 95% Confidence Intervals are two-sided and calculated using the binomial distribution

Table A 22. GCRS responder rate by treatment at Week 4, Month 3 and Month 6, Treating Investigator (FAS)

Time point	Treatment group	# of subjects in FAS with non-missing values	# of responders	Proportion of responders	95% confidence interval	P-value
4 Week	Restylane Defyne	xx	xx	x.xx	x.xx, x.xx	
	Control	xx	xx	x.xx	x.xx, x.xx	
	Difference	-		x.xx	x.xx, x.xx	x.xx
3 Month	Restylane Defyne	xx	xx	x.xx	x.xx, x.xx	
	Control	xx	xx	x.xx	x.xx, x.xx	
	Difference	-		x.xx	x.xx, x.xx	x.xx
6 Month	Restylane Defyne	xx	xx	x.xx	x.xx, x.xx	
	Control	xx	xx	x.xx	x.xx, x.xx	
	Difference	-		x.xx	x.xx, x.xx	x.xx

Note: Subjects with a missing GCRS are not imputed

Note: Responder is defined as a subject with an improvement of at least one grade on the GCRS from baseline

Note: Responder rate is calculated as the number of Responders divided by the number of subjects in the FAS population for the specific treatment group.

Note: P-values for the difference in proportions are based on the Fisher's Exact test

Note: 95% Confidence Intervals are two-sided and calculated using the binomial distribution

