2.2 Analysis Populations

The following populations will be defined:

- Safety Includes all subjects who were treated with Restylane Defyne or randomized to no-treatment group. Subjects are analyzed based on the as treated principle
- Full Analysis Set (FAS) Includes all subjects who were treated with Restylane Defyne or randomized to no-treatment group. Subjects are analyzed according to the randomization assignment.
- Per Protocol (PP) Includes all subjects in FAS that comply to the protocol procedures with no deviations that can affect the evaluation of the primary variable

The FAS population is the primary population for all effectiveness analyses. All safety analyses will be based on the Safety population.

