2.3.2 Withdrawals and Protocol deviations

All withdrawn subjects will be listed individually, including at least subject number, date and reason for withdrawal, and last visit performed. Subjects with CSP deviations will be listed individually, including subject number and observed deviation. Depending on the seriousness of the deviation, subject might be excluded from the PP population, which shall be documented prior to database lock.

 GALDERMA	Title Statistical Analysis Plan 43CH1627 - Chin	Doc id MA-38115
--	---	---------------------------

For this study, the protocol deviations that will exclude subjects from PP are identified (but not limited to) in Table 3 below.

Table 3. Protocol deviations

	Deviation
GENERAL	
	Visit out-of-window
	* Follow-up at Month 6 after last treatment performed earlier than 1 week before or later than 2 weeks after the scheduled visit for the treatment group
	* Follow-up at Month 6 after randomization performed earlier than 1 week before or later than 2 weeks after the scheduled visit for the control group
EFFECTIVENESS	
	Primary effectiveness endpoint
	* Pre-treatment GCRS by blinded evaluator not done
	* GCRS by blinded evaluator missing at Month 6 after last treatment for treatment group
	* GCRS by blinded evaluator not done at Month 6 after randomization for control group
	Treatment
	* Wrong treatment given at baseline
OTHER	
	Inclusion/exclusion criteria
	* Violate any inclusion or exclusion criteria considered to have substantial effect on the primary effectiveness endpoint
	Concomitant medication/procedures
	* Take any prohibited concomitant medication/procedures considered to have substantial effect on the primary effectiveness endpoint

Deviations from the SAP will be documented in the CSR.

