2.4 Effectiveness analysis

2.4.1 Datasets analyzed

[figure not shown]
All effectiveness variables will be analyzed using the FAS population. The primary analysis will be repeated using the PP population. If it is deemed necessary, other analyses will be repeated using the PP population.

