2.4.2 Handling of missing data

Number of missing values will be summarized and reported as appropriate. The baseline observation carried forward (BOCF) method will be used as the primary method to handle missing data on the primary effectiveness variable at the Month 6 visit in the FAS analysis set. This strategy is a conservative approach as it treats subjects with missing data as non-responders. Impact of missing data on the primary analysis for Month 6 endpoint will be evaluated by performing sensitivity analysis based on the PP population. In addition, missing data for the primary analysis will also be handled using the hot deck method.

All other endpoints will be analyzed on available data, i.e. no imputations will be done.

CCI

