2.4.3 Primary effectiveness analysis

The responder rate will be calculated for each group at Month 6 (after last treatment in Treatment Group and after randomization in Control group) based on the blinded evaluator's assessment. The responder rate in the Treatment Group will then be compared with the responder rate in the Control Group using a Fisher's exact test at a significance level of 5%. In addition, for each group the two-sided 95% confidence interval around the estimates of the percentage of responders will also be calculated. The treatment will be deemed a success if the p-value for the treatment difference on the primary endpoint is less than 0.05.

In order to assess robustness of the conclusions of the primary endpoint analysis, a logistic regression will be utilized, including baseline GCRS and treatment group as factors. The overall treatment effect will be used for assessing the robustness of the result of the primary analysis when corrected for baseline GCRS.

In addition, to obtain an estimate of the true clinical treatment effect, the primary analysis will be re-run using the PP analysis set.

 GALDERMA	Title Statistical Analysis Plan 43CH1627 - Chin	Doc id MA-38115
--	---	---------------------------

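### SAP Tables A 18, A 21 and A 22 divide responders by the whole FAS although none of them imputes, so followed literally they understate the responder rates

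*SAP*

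**What the plan says.** **Table A 17 (primary, FAS, BOCF).** The note reads "Responder rate is calculated as the number of Responders divided by the number of subjects in the FAS population for the specific treatment group". Table A 19 (hot deck) uses the same note. In both tables every FAS subject is given a value, so the denominator fits.

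**Table A 18 (PP).** Its first note is "No imputation is used for the PP analysis. Only subjects with complete data are included". The denominator note that follows is nevertheless the FAS one. The layout is taken over from Table A 17 by reference, so the subject-count column is also headed as FAS.

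**Tables A 21 (Blinded Evaluator, Month 3) and A 22 (Treating Investigator, Week 4, Month 3, Month 6).** Both say that missing scores are not imputed, and both repeat the FAS denominator note. A 21 also inherits the A 17 column. A 22 has its own column heading, which counts only FAS subjects with a value.

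**The body of the SAP.**
- Section 2.4.1: "The primary analysis will be repeated using the PP population".
- Section 2.4.2: "Impact of missing data on the primary analysis for Month 6 endpoint will be evaluated by performing sensitivity analysis based on the PP population", and then "In addition, missing data for the primary analysis will also be handled using the hot deck method". The same section, like protocol 10.6, puts every endpoint other than the primary on available data.
- Section 2.4.3: "In addition, to obtain an estimate of the true clinical treatment effect, the primary analysis will be re-run using the PP analysis set".
- Section 2.2 defines PP as a subset of FAS: "Includes all subjects in FAS that comply to the protocol procedures with no deviations".
- Table 3 in section 2.3.2 removes, among others, subjects with "GCRS by blinded evaluator missing at Month 6 after last treatment for treatment group" and subjects seen outside the Month 6 window.

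**The concern.** Dividing by all FAS subjects counts everyone without a usable score as a non-responder. That is imputation in effect, in three tables that say there is none.

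The consequences differ by table:

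- **A 18.** The PP rate is meant to show how far missing data drive the primary result and to give an effect estimate in compliant subjects. With the FAS denominator it is pulled back towards the BOCF result it is supposed to check.
- **A 21.** Table A 23 reports the same Blinded Evaluator rate at Month 3 over subjects with a value. The report would show two rates for one quantity.
- **A 22.** The printed rate would not equal the responder count divided by the n in the same row.

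In A 22 the heading might alert a programmer. In A 18 and A 21 the inherited column and the note agree with each other, so nothing within the layout signals the mistake.

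**Working it through.** **Inputs.** SAP 1.1.2 and 2.7 give 148 subjects randomized 3:1, arms of about 111 and 37, and a 15% drop-out allowance. Check: 148 × 3/4 = 111 and 148/4 = 37. The allowance leaves 0.85 × 111 = 94.35 and 0.85 × 37 = 31.45, so about 94 and 31; inflating back, 94/0.85 = 110.6 and 31/0.85 = 36.5, which round up to 111 and 37. The planning response rates and evaluable numbers are redacted and the PP size is unknown. All responder counts and losses below are therefore assumptions, shown as a range. The 15% case is an upper illustration.

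**Step 1: size of the error in one arm.** Let r be responders among the n subjects analysed, and N the FAS size. The intended rate is r/n. The rate under the note is r/N = (r/n) × (n/N). It is lower whenever n < N and r ≥ 1. If r = 0 or n = N, nothing changes.

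Treatment arm, N = 111; each cell shows r, then r/n → r/N:

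| Excluded or missing | n | about 50% | about 65% | about 80% | about 95% |
|---|---|---|---|---|---|
| 2 (1.8%) | 109 | 54: 49.5 → 48.6 | 71: 65.1 → 64.0 | 87: 79.8 → 78.4 | 104: 95.4 → 93.7 |
| 6 (5.4%) | 105 | 52: 49.5 → 46.8 | 68: 64.8 → 61.3 | 84: 80.0 → 75.7 | 100: 95.2 → 90.1 |
| 17 (15.3%) | 94 | 47: 50.0 → 42.3 | 61: 64.9 → 55.0 | 75: 79.8 → 67.6 | 89: 94.7 → 80.2 |

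Shortfalls from unrounded rates: 0.9 / 1.2 / 1.4 / 1.7 points, 2.7 / 3.5 / 4.3 / 5.1 points, and 7.7 / 9.9 / 12.2 / 14.5 points.

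Control arm, N = 37, 6 excluded or missing: 0/31 stays 0%; 3/31 = 9.7% becomes 3/37 = 8.1%; 6/31 = 19.4% becomes 6/37 = 16.2%.

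**Step 2: the group difference.** It has no fixed direction.

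- 75/94 against 3/31: 79.8 − 9.7 = 70.1 points. As written: 67.6 − 8.1 = 59.5.
- 47/94 against 6/31: 50.0 − 19.4 = 30.6. As written: 42.3 − 16.2 = 26.1.
- Loss in Control only, 89/111 against 3/31: 80.2 − 9.7 = 70.5. As written: 80.2 − 8.1 = 72.1.

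**Step 3: A 18 against A 17.** PP is a subset of FAS, so PP responders cannot outnumber the responders counted in A 17. Both counts would be divided by the same N, so the A 18 rate is at most the A 17 rate in each arm. They are equal when no A 17 responder is excluded from PP. With 17 of 111 Treatment subjects excluded and 75 responders in PP:

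- None of the 17 is a responder in A 17: A 17 = 75/111 = 67.6%, A 18 as written = 67.6%, real PP rate = 75/94 = 79.8%. The check would show no change when the PP rate is 12.2 points higher.
- Five of the 17 are responders (for example seen out of window): A 17 = 80/111 = 72.1%, A 18 as written = 67.6%, real PP rate = 79.8%. The printed PP rate would be below the primary rate when it is in fact above it.

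**The case against.** The strongest reply is that this is a carried-over footnote in mock tables, and that the governing text is clear. Sections 2.4.1 to 2.4.3 fix the PP set and the available-data rule, the A 18 title says PP, and A 22's column already counts the right subjects. A careful programmer would use the right denominators, a reader of A 22 could recompute the rate from its row, and losses by Week 4 or Month 3 may be small.

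Much of this stands. The harm arises only if the notes are followed, and with few losses it is one or two points. The notes define only the rate, so no effect on the Fisher p-values is claimed. The hot deck analysis in Table A 19 remains a separate missing-data check. What is impaired is the printed PP proportion, not every use of the PP run.

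It does not remove the point. The note is an explicit calculation rule, and in A 18 and A 21 the inherited column supports it. The body text shows which denominator is meant, which makes the notes wrong as written rather than merely incomplete.

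It could also be asked whether Table A 23 shares the fault, since it imputes at Month 6 yet divides by subjects with non-missing values. Once BOCF has filled the Month 6 gaps no value is missing, so that denominator equals the FAS and agrees with A 17.

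**Conclusion.** The concern holds. The denominator notes to Tables A 18, A 21 and A 22 contradict the analysis rules those tables are meant to follow. Taken literally, they scale each arm's rate by n analysed over n FAS. For A 18 the loss that counts is any exclusion from PP, not only a missing score; for A 21 and A 22 it is a missing score at the visit.

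The size depends on losses that cannot be known in advance and on response rates that are redacted. Over assumed Treatment rates of about 50% to 95%, the understatement runs from about 1 to 2 points with 2 subjects lost to about 8 to 15 points at the full drop-out allowance. The printed PP rate would be unreliable for the two purposes the SAP gives it. The primary result, the success rule and Tables A 17, A 19 and A 23 to A 25 are not touched. It should be fixed, but it does not threaten the trial's main conclusion.

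**What to change.** - **Table A 18:** make the denominator the number of PP subjects in the group, in both the note and the column inherited from A 17.
- **Table A 21:** make it the number of FAS subjects with a non-missing GCRS at Month 3, in both the note and the inherited column.
- **Table A 22:** change the note to FAS subjects with a non-missing GCRS at that visit, so that it matches the existing heading.
- Leave Tables A 17, A 19 and A 23 to A 25 as they are.

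The cost is three corrected notes and two column headings in the SAP shells. No extra data or analysis is needed.

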**Table A 23. GCRS responder rate over time at Month 3 and Month 6, Blinded Evaluator (FAS)**

Time point	Treatment group	# of subjects in FAS with non-missing values	# of responders	Proportion of responders	95% confidence interval
3 Months after last treatment	Restylane Defyne	xx	xx	X.XX	X.XX, X.XX
3 Months after randomization	Control	xx	xx	X.XX	X.XX, X.XX
	Difference	-		X.XX	X.XX, X.XX
6 Months after last treatment	Restylane Defyne	xx	xx	X.XX	X.XX, X.XX
6 Months after randomization/treatment	Control	xx	xx	X.XX	X.XX, X.XX
	Difference	-		X.XX	X.XX, X.XX

Note: Missing GCRS are imputed at Month 6

Note: Responder is defined as a subject with an improvement of at least one grade on the GCRS from baseline

Note: Responder rate = # of Responders/# of subjects in FAS with non-missing values

Note: Subjects in Control group receive optional treatment at Month 6 after randomization

Table A 24. GCRS responder rate over time, Blinded Evaluator (FAS)

Time point	Treatment group	# of subjects in FAS with non-missing values	# of responders	Proportion of responders	95% confidence interval
9 Months after last treatment	Restylane Defyne	xx	xx	X.XX	X.XX, X.XX
12 Months after last treatment	Restylane Defyne	xx	xx	X.XX	X.XX, X.XX
3 Months after last treatment	Control	xx	xx	X.XX	X.XX, X.XX
6 Months after last treatment	Control	xx	xx	X.XX	X.XX, X.XX
9 Months after last treatment	Control	xx	xx	X.XX	X.XX, X.XX
12 Months after last treatment	Control	xx	xx	X.XX	X.XX, X.XX

Note: Missing GCRS are not imputed

Note: Responder is defined as a subject with an improvement of at least one grade on the GCRS from baseline

Note: Responder rate = # of Responders/# of subjects in FAS with non-missing values

Note: Subjects in Control group receive optional treatment at Month 6 after randomization

Table A 25. GCRS responder rate over time, Treating Investigator (FAS)

As Table A 24.

Note: Missing GCRS are not imputed

Note: Responder is defined as a subject with an improvement of at least one grade on the GCRS from baseline

Note: Responder rate = # of Responders/# of subjects in FAS with non-missing values

Note: Subjects in Control group receive optional treatment at Month 6 after randomization

Title

Statistical Analysis Plan 43CH1627 - Chin

Doc id

MA-38115

CCI

